9.3.2 Pharmacokinetic Statistical Methodology

Log-transformed C_{\max} , $AUC(0-\infty)$, and $AUC(0-t_{\text{last}})$ estimates will be evaluated in a linear fixed-effect model with a fixed effect for formulation. Whether injection site leakage occurred (yes/no) may also be included in the model as a covariate if leakage occurs frequently. Furthermore, if this is found to be significant, the amount of leakage will also be added to the model. The formulation differences will be back-transformed to present the ratios of geometric least squares means and the corresponding 90% CI.

A single linear model with contrasts will be used for all of the following comparisons:

- Relative bioavailability of formulations: Test SC 2 \times 1-mL versus Reference

- Relative bioavailability of number of injections: Test SC $2 \times 1\text{-mL}$ versus Test SC $1 \times 2\text{-mL}$

If the number of injections is not observed to have an effect based on the above analysis, the following comparison will evaluate absolute bioavailability (on $\text{AUC}[0-\infty]$, and $\text{AUC}[0-t_{\text{last}}]$ only):

- Test SC (combined data from SC $2 \times 1\text{-mL}$ and SC $1 \times 2\text{-mL}$) versus Test IV

If the number of injections is observed to have an effect, analyses to evaluate absolute bioavailability will be done separately:

- Test SC $1 \times 2\text{-mL}$ versus Test IV
- Test SC $2 \times 1\text{-mL}$ versus Test IV

If the number of injections is observed to have an effect, the primary analysis of absolute bioavailability will be considered as that including SC $1 \times 2\text{-mL}$.

Example SAS code:

```
proc mixed data=pk;
  by parameter;
  class formulation ISLoccur;
  model log_pk = formulation ISLoccur ISLamount / residual ddfm=kr;
  lsmeans formulation / alpha=0.1 cl pdiff;
  ods output lsmeans=lsmeans;
  ods output diffs=diffs;
run;
```

The t_{max} will be analyzed using a Wilcoxon rank sum test for the relative bioavailability comparisons. Estimates of the median difference, 90% CIs, and p-values from the Wilcoxon rank sum test will be calculated.

Additional analyses may be conducted if they are deemed appropriate.

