| Injection site pain based on Visual analog scale (VAS) (hour) | | | 0, 0.5, 1, 3, 6 | 24 | | | | | | | | | | | | Performed only on subjects randomized to Test SC 2 x 1 mL (assessed for the first of 2 injections) and Test SC 1 x 2 mL only. 0 hour assessments should be performed within 1 minute after injection. Time allowance for 0.5 and 1 hour will be ± 5 minutes and all other time allowance will be ± 15 minutes. |
| Injection site leakage and bleeding assessment (hour) | | | 0 | | | | | | | | | | | | | Performed only on subjects randomized to Test SC 2 x 1 mL and Test SC 1 x 2 mL only. 0 hour assessments should be performed within 1 minute after injection. |
| LY3074828 PK sampling (hour) | | | 0, end of infusion ^b , 2, 6 | 24 | 72 | 168 | 240 | 336 | 504 | 672 | 1008 | 1344 | 1680 | 2016 | X | Times are referenced to start of dosing. 0 hour collection should be taken immediately (within 15 minutes) before dosing. The end of infusion sampling should be taken at the end of IV infusion. Time allowance for 2, 6, and 24 hour time points will be ± 15 , ± 30 , and ± 90 minutes respectively. |

| Study Day | Screening ≤ 28 days | -1 | 1 | 2 ±1d | 4 ±1d | 8 ±2d | 11 ^a ±2d | 15 ±2d | 22 ±2d | 29 ±2d | 43 ±2d | 57 ±3d | 71 ±3d | 85 ±3d | FU/ED ^d | Comment |
|-------------------------|------------------------|----|---------|----------|----------|----------|------------------------|-----------|-----------|-----------|-----------|-----------|-----------|-----------|---------------------------|---------|
| Immunogenicity sample | | | Predose | | | | X | | X | | | | X | X | LY3074828 antibody sample | |
| Pharmacogenetics sample | | X | | | | | | | | | | | | | For storage only. | |

Abbreviations: AE = adverse event; CRU = clinical research unit; d = day; ECG = electrocardiogram; ED = early discontinuation; FU = follow-up visit; ICF = informed consent form; IV = intravenous; PK = pharmacokinetic; TB = tuberculosis; VAS = visual analog scale.

Site should schedule activities as appropriate. In cases where several study procedures are scheduled at the same time, follow this order of priority for procedures: PK samples, ECG, vital signs, clinical laboratory tests, VAS, injection site leakage assessment, injection / infusion site assessment, immunogenicity sample, stored sample. Procedures specified as predose may be performed within 2 hours from planned dosing.

- a Day 11 required for subjects receiving subcutaneous treatments only.

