The Lilly clinical pharmacologist or clinical research physician/scientist will monitor safety data throughout the course of the study.

Lilly will review SAEs within time frames mandated by company procedures. The Lilly clinical pharmacologist or research physician will consult with the functionally independent Global Patient Safety therapeutic area physician or clinical research scientist when appropriate, and periodically review:

- trends in safety data
- laboratory analytes
- AEs including monitoring of incidence of and nature of any infections, infusion reactions, and injection site reactions.

9.4.6. *Injection / Infusion-Site Assessments*

Local tolerability at the injection or infusion site will be evaluated for erythema, induration, categorical pain, pruritus, and edema as indicated in the Section 2 and reported in the CRF. If one or more symptom(s) of an injection/infusion site reaction is reported during the assessment, a single AE for injection or infusion site reaction will be recorded on the AE page of the CRF.

In addition, pain measurements will be quantified using the the 100-mm validated Visual Analog Scale (VAS) for the subjects receiving Test SC 2 x 1 mL and the Test SC 1 x 2 mL formulation. The VAS is a well-validated tool (Williamson and Hoggart 2005) to assess injection-site pain presented as a 10-cm (100-mm) line, anchored by verbal descriptors, usually “no pain” and “worst imaginable pain.” The patient will be asked to rate any pain on a scale of 0 to 100 mm on the line immediately (within 1 minute) following the start of the injection and at time points according to the Schedule of Activities (Section 2). For the Test SC 2 x 1 mL formulation, the pain assessment will be done only for the first of the 1 mL injections.

Injection site leakage for the Test SC 1 x 2 mL and the first of the Test SC 2 x 1 mL injections will be assessed using pre-weighed filter paper, blotting the injection site immediately after the injection to absorb any post-injection leakage and placing the filter paper back on the tared analytical balance in a similar manner as previously described (Ignaut and Fu 2012). For the Test SC 2 x 1 mL formulation, the leakage assessment will be done only for the first of the 1 mL injections. The amount of leakage will be calculated by subtracting the pre-weighed filter paper measurement from the post-injection site blot filter paper measurement. Any bleeding from the injection site will also be documented.

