10.3.2.2. Pharmacokinetic Statistical Inference

Pharmacokinetic parameter estimates will be evaluated to delineate effects of LY3074828 formulation when administered to healthy subjects by SC injection (Reference and Test SC 2 × 1-mL). Log-transformed C_{max} , $AUC(0-\infty)$, and $AUC(0-t_{last})$ estimates will be evaluated in a linear fixed-effect model with a fixed effect for formulation. The differences between the test (SC 2 × 1-mL) compared to the reference formulation will be back-transformed to present the ratios of geometric least squares means and the corresponding 90% CI.

The t_{max} will be analyzed using a Wilcoxon rank sum test. Estimates of the median difference, 90% CIs, and p-values from the Wilcoxon rank sum test will be calculated.

Similar analyses to those described above will be conducted to delineate the effect of administering the same volume as a single injection (SC $1 \times 2\text{-mL}$) or as 2 injections (SC $2 \times 1\text{-mL}$).

In order to evaluate absolute bioavailability, a fixed-effect model will be used to analyze the log-transformed $\text{AUC}(0-\infty)$ and $\text{AUC}(0-t_{\text{last}})$ of LY3074828. The model will contain formulation (SC or IV) as a fixed effect. The absolute bioavailability will be estimated for the ratio of the least-squares geometric means of the formulations (SC/IV). The corresponding 90% CI of the ratios will also be estimated. Data from Test IV will be used for the IV formulation (reference). If the number of injections is not observed to have an effect based on the analyses described above, data from SC $2 \times 1\text{-mL}$ and SC $1 \times 2\text{-mL}$ will be combined and used for the SC formulation (and will be considered the primary analysis). If the number of injections is observed to have an effect (ie, SC $2 \times 1\text{-mL}$ versus SC $1 \times 2\text{-mL}$), analyses to evaluate absolute bioavailability will be done separately (SC $2 \times 1\text{-mL}$ versus IV and SC $1 \times 2\text{-mL}$ versus IV). The primary analysis will be considered as that including SC $1 \times 2\text{-mL}$.

Where possible, a single linear model with contrasts to test the different objectives will be used. Additional analyses may be conducted if they are deemed appropriate.

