9.4.8 Injection Site Leakage

Injection site leakage data will be listed. Any bleeding from injection site will also be documented (performed only on subjects randomized to Test SC 2 × 1 mL and Test SC 1 × 2 mL).

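### SAP 9.3.2 lets leakage, measured only in the two Test SC arms, enter the four-arm PK model; the primary contrast is then lost or adjusted on the Test side only

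*SAP*

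**What the plan says.** The default model has formulation as its only effect. This matches Protocol 10.3.2.2, where the log-transformed "estimates will be evaluated in a linear fixed-effect model with a fixed effect for formulation".

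SAP 9.3.2 then adds an option that the protocol does not have: "Whether injection site leakage occurred (yes/no) may also be included in the model as a covariate if leakage occurs frequently". If that term is significant, the amount of leakage is added as well. Neither the frequency that triggers the first step nor the significance level for the second is given. The example code carries both terms, with no restriction by arm: "model log_pk = formulation ISLoccur ISLamount / residual ddfm=kr".

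The same section states "A single linear model with contrasts will be used for all of the following comparisons". These include the primary Test SC 2 × 1-mL versus Reference. It also uses the injection-number contrast to choose the absolute bioavailability analysis: "If the number of injections is not observed to have an effect based on the above analysis, the following comparison will evaluate absolute bioavailability".

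Leakage data exist for two arms. The leakage row of the Schedule of Activities (Protocol 2) reads "Performed only on subjects randomized to Test SC 2 x 1 mL and Test SC 1 x 2 mL only". Protocol 9.4.6 narrows this further: "For the Test SC 2 x 1 mL formulation, the leakage assessment will be done only for the first of the 1 mL injections". SAP 9.4.8 names the same two arms. Neither document says how leakage is to be coded for Reference or Test IV.

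**The concern.** A covariate that is unmeasured in half the arms cannot adjust comparisons between those arms and the others. What happens depends on a coding choice that the SAP leaves open.

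- **Missing, or a separate not-assessed level.** The covariate is confounded with arm, and the primary contrast and all SC-versus-IV contrasts disappear. The output would show this.
- **Coded no/0.** Everything can be estimated, but the leakage coefficient is learned in the Test SC arms and applied only there. Reference is given as three SC injections, and any leakage in it stays in its mean. Nothing in the output would show this. For Test IV a zero is defensible, but the SC/IV ratio then describes bioavailability without leakage.

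Leakage is also observed after randomisation and dosing. It may be one route by which one injection differs from two. Adjusting the 2 × 1-mL versus 1 × 2-mL contrast for it can remove part of the effect under study, and that contrast decides whether the SC arms are pooled.

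**Working it through.** **Inputs.** 16 completers in each of four arms, 72 enrolled, CV 49% and a planned 90% CI half-length of 0.28 on the log scale (all SAP 7). The documents give no leakage rate and no loss of exposure from leakage, so both are assumed below.

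**1. The plan's precision.** Log SD = √ln(1 + 0.49²) = 0.464. SE of a two-arm difference = 0.464 × √(2/16) = 0.164. Half-length = 1.671 × 0.164 = 0.274 with 60 residual df, or 0.278 with the 30 df of two arms. The 28% is therefore reproduced as the half-length at the assumed SD. It is not reproduced as a bound met with 90% probability (that would be 0.305 with 60 df). That is a separate matter; 0.28 serves here only as a yardstick.

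**2. Estimability.** A contrast L is estimable if it lies in the row space of the design matrix X (intercept, four arms, leakage levels). Results with 16 per arm:

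| Coding of Reference and IV | Records | Rank | 2 × 1 vs Reference | SC vs IV | 2 × 1 vs 1 × 2 |
|---|---|---|---|---|---|
| Missing | 32 | 3 | no | no | yes |
| Separate level | 64 | 5 | no | no | yes |
| No/0 | 64 | 5 | yes | yes | yes |

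Adding the amount to the no/0 coding raises the rank to 6 and changes no entry. Under missing coding the residual df fall from 64 − 4 = 60 to 32 − 3 = 29; with all 72 dosed, from 68 to 36 − 3 = 33. The yes entries assume that at least one Test SC arm has both leakers and non-leakers.

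**3. Shift under no/0 coding.** Every Reference record has leakage 0, so its fitted mean is its raw mean. The Test 2 × 1-mL mean becomes raw mean − b × p, where b is the leakage coefficient and p the share leaking in that arm. If leakers lose a fraction ℓ of exposure, b = ln(1 − ℓ), and the log ratio shifts by −p × ln(1 − ℓ). This was compared with simulation: 8,000 trials per scenario, no true formulation effect, Reference leaking at the 2 × 1-mL rate, and 1 × 2-mL leaking at 60% (30% rows) or 50% (50% rows).

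| p | ℓ | Formula | Simulated | Change in ratio |
|---|---|---|---|---|
| 30% | 0% | 0 | 0.000 | none |
| 30% | 2% | 0.006 | 0.005 | +0.5% |
| 30% | 10% | 0.032 | 0.031 | +3% |
| 50% | 10% | 0.053 | 0.052 | +5% |
| 30% | 20% | 0.067 | 0.066 | +7% |
| 50% | 20% | 0.112 | 0.111 | +12% |

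The largest shift is about two thirds of the SE of 0.164, and 0.111/0.28 = 40% of the planned half-length. In these scenarios Test and Reference leak alike, so the whole shift is bias. If Reference did not leak, the adjusted contrast would instead estimate a no-leakage comparison. The trial collects nothing that could tell the two apart.

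**4. Precision under no/0 coding.** Variance = σ² × (2/16 + p²/S), where S is the sum of 16p(1 − p) over the two Test SC arms. With 8 of 16 leaking in each, S = 8 and the half-length is 1.671 × 0.464 × √(0.125 + 0.25/8) = 0.306, against 0.274 unadjusted. With 4 or 12 of 16 it is 0.285 or 0.363. In the simulation the SE rises from 0.164 to 0.173 (30% leaking) or 0.186 (50%), even when leakage is harmless.

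**5. Injection-number contrast.** With 30% leaking in 2 × 1-mL and 60% in 1 × 2-mL, adjustment moves the log difference (1 × 2 minus 2 × 1) from −0.034 to −0.003 at 10% loss, and from −0.071 to −0.005 at 20%. Nearly all of a difference produced by the injection scheme is removed, though both movements are small against an SE of about 0.17.

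**6. The significance step.** At an assumed 5% level the yes/no term is significant in 5% to 25% of simulated trials. In those trials, with 10% to 20% loss, the mean shift is 0.11 to 0.21. Selection on significance inflates these values, so the table in step 3 is the fairer measure.

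**The case against.** The option is doubly conditional: leakage must be frequent, and even then it only may be included. The formulation-only model is stated first and the code is headed as an example. If the option is never used, nothing changes. This stands and limits the severity. However, the SAP does not say that the unadjusted result would still be reported, and a pre-specified option should work when it is triggered.

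The upper end of the range is demanding. The 2 × 1-mL arm receives 2 mL and only its first 1-mL injection is assessed. A 20% loss from that injection alone would be 0.4 mL, or 40% of it; a 10% loss would be 20% of it. At 2% loss the shift is about 0.005, roughly 3% of an SE. This also stands, so the small shifts should be read alongside the large ones. It does not touch the loss of the primary contrast under the other two codings, which does not depend on size.

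The shifts in significant trials come from a model without the amount, which the SAP would then add. A further run with the amount included moved the mean shift in those trials by 0.002 or less.

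The frequency trigger can be judged without PK results, so data-driven choice is a real concern mainly at the amount step. The exceptions to estimability, where every subject in a Test SC arm leaks, are real but make the option work less well.

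**Conclusion.** The point holds, and the option is wrong as written. Once leakage enters the single model, no coding of the unassessed arms preserves the protocol's primary contrast. It is either non-estimable or adjusted on the Test side only.

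The non-estimability follows from the design and needs no assumed rate. The size of the one-sided shift does: 0 to 0.111 on the log scale for leakage in 30% to 50% of subjects and losses of 0% to 20%, with some loss of precision throughout. If leakage does not affect exposure there is no bias. The study reports ratios with 90% CIs and has no pass/fail margin, so the cost is a lost or shifted estimate rather than a wrong decision. It should be fixed, but it does not threaten the trial if the default model is used.

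**What to change.** In SAP 9.3.2, state that log(PK) = formulation, as in Protocol 10.3.2.2, is the model for all planned contrasts and for the decision to pool the SC arms. Delete the two sentences on leakage occurrence and amount, and remove ISLoccur and ISLamount from the class and model statements of the example code.

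If leakage is still of interest, confine any adjusted or by-leakage analysis to a sensitivity or descriptive analysis within the two Test SC arms. Note there that only the first 2 × 1-mL injection is assessed. List that analysis in SAP Section 11, which at present declares no changes from the protocol.

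The cost is SAP wording and two code statements. No new data and no protocol amendment are needed.

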| Regimen | 250 mg SC ^a | 250 mg SC | 250 mg SC | 250 mg IV |
| Drug Product formulation | reference | test | test | test |
| LY3074828 concentration | 72 mg/mL | 125 mg/mL | 125 mg/mL | 250 mg/10 mL (25 mg/mL) |
| Volume per dose | 2 × 1 mL + 1 × 1.5 mL (3.5 mL total) | 2 × 1 mL (2 mL total) | 1 × 2 mL (2 mL total) | 10 mL infusion |
| Infusion or injection duration | NA | NA | Slow versus fast ^b | ≥30 minutes |

Abbreviations: IV = intravenous; NA = not applicable; SC = subcutaneous.

a Theoretical total dose 252 mg for Reference.

b Odd number subjects will be injected slowly, approximately over 15 seconds and even number subjects will receive the injection over 5 to 10 seconds.

The investigator or designee is responsible for:

- explaining the correct use of the investigational product(s) to the site personnel,
- verifying that instructions are followed properly,
- maintaining accurate records of investigational product dispensing and collection,
- and returning all unused medication to Lilly or its designee at the end of the study.

Note: In some cases, sites may destroy the material if, during the investigative site selection, the evaluator has verified and documented that the site has appropriate facilities and written procedures to dispose of clinical trial materials.

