10.1. Sample Size Determination

A total of 72 subjects will be enrolled to ensure that approximately 64 subjects complete the study (16 completers per treatment). The estimated total variability (coefficient of variation) in AUC from time zero to infinity (AUC[0-∞]), AUC from time zero to time t , where t is the last sample with a measurable concentration (AUC[0- t_{last}]), and maximum observed drug concentration (C_{max}) was 49%, 49%, and 23%, respectively, in Study AMAA following a single SC dose of 120 mg LY3074828. The coefficient of variation of 49% was used for precision estimates and is assumed for all treatment arms. A sample size of 64 subjects will provide a precision of approximately 28% for the geometric means ratio in AUC(0-∞), AUC(0- t_{last}), and C_{max} of reference to test in log scale. That is, there is a 90% probability that the half-length of the 90% confidence interval (CI) of the geometric means ratio in log scale is not larger than 28%.

Subjects who are randomized but not administered treatment may be replaced to ensure that approximately 64 subjects may complete the study.

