7. SAMPLE SIZE JUSTIFICATION

A total of 72 subjects will be enrolled to ensure that approximately 64 subjects complete the study (16 completers per treatment). The estimated total variability (coefficient of variation) in AUC from time zero to infinity ($AUC[0-\infty]$), AUC from time zero to time t , where t is the last sample with a measurable concentration ($AUC[0-t_{last}]$), and maximum observed drug concentration (C_{max}) was 49%, 49%, and 23%, respectively, in Study AMAA following a single SC dose of 120 mg LY3074828. The coefficient of variation of 49% was used for precision estimates and is assumed for all treatment arms. A sample size of 64 subjects will provide a precision of approximately 28% for the geometric means ratio in $AUC(0 -\infty)$, $AUC(0-t_{last})$, and C_{max} of reference to test in log scale. That is, there is a 90% probability that the half-length of the 90% confidence interval (CI) of the geometric means ratio in log scale is not larger than 28%.

Subjects who are randomized but not administered treatment may be replaced to ensure that approximately 64 subjects may complete the study.

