8. DEFINITION OF ANALYSIS POPULATIONS

The “Safety” population will consist of all subjects who received study drug, and have at least one postdose safety assessment.

The “Pharmacokinetic” population will consist of all subjects who received study drug and have evaluable PK data.

All protocol deviations that occur during the study will be considered for their severity/impact and will be taken into consideration when subjects are assigned to analysis populations.

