9. STATISTICAL METHODOLOGY

9.1 General

Data listings will be provided for all data that is databased. Summary statistics and statistical analysis will only be presented for data where detailed in this SAP. For continuous data, summary statistics will include the arithmetic mean, arithmetic standard deviation (SD), median, min, max and N; for log-normal data (e.g. the PK parameters: AUCs and C_{max}) the geometric mean and geometric coefficient of variation (CV%) will also be presented. For categorical data, frequency count and percentages will be presented. Data listings will be provided for all subjects up to the point of withdrawal, with any subjects excluded from the relevant population highlighted. Summary statistics and statistical analyses will generally only be performed for subjects included in the relevant analysis population. For the calculation of summary statistics and statistical analyses, unrounded data will be used.

Mean change from baseline is the mean of all individual subjects' change from baseline values. Each individual change from baseline will be calculated by subtracting the individual subject's baseline value from the value at the timepoint. The individual subject's change from baseline values will be used to calculate the mean change from baseline using a SAS procedure such as Proc Univariate.

Data analysis will be performed using SAS® Version 9.3 or greater.

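### Cheap improvement: on its natural reading, the model behind the primary AUC interval uses one residual variance, half of it from arms outside the contrast, with no IV variability data to support equal spread

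*SAP*

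**What the plan says.** SAP 9.3.2 fits the log-transformed PK parameters with a fixed effect for formulation and reports ratios of geometric least squares means with 90% intervals. It introduces its list of contrasts with "A single linear model with contrasts will be used for all of the following comparisons". Two SC contrasts follow: Test SC 2 × 1-mL against Reference (the primary objective) and Test SC 2 × 1-mL against Test SC 1 × 2-mL. The comparison with Test IV comes next, on the AUCs only. Its form depends on a condition that begins "If the number of injections is not observed to have an effect based on the above analysis".

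The example PROC MIXED step contains "model log_pk = formulation ISLoccur ISLamount / residual ddfm=kr". It has no arm filter and no REPEATED / GROUP= statement, so it estimates one residual variance. The two leakage terms are optional in the text.

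On variability, Protocol 10.1 says: "The coefficient of variation of 49% was used for precision estimates and is assumed for all treatment arms". SAP 7 gives the source as observed "in Study AMAA following a single SC dose of 120 mg LY3074828". Protocol 3.2 shows that this SC cohort had 5 healthy subjects. Neither document reports a CV after IV dosing.

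SAP 9.1 says that for log-normal PK parameters "the geometric mean and geometric coefficient of variation (CV%) will also be presented", but the plan states no rule for what to do if the arms differ in spread.

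**The concern.** No equivalence margin is set, so the 90% interval for the AUC ratio is itself the primary result. Its stated level depends on equal variance across arms, including arms that the contrast does not compare. The IV arm bypasses SC absorption, and the documents give no basis for assuming that its spread equals that of the SC arms. Test SC 1 × 2-mL also differs in one respect: Table AMAL.3 of the Protocol gives it two injection speeds ("Odd number subjects will be injected slowly, approximately over 15 seconds and even number subjects will receive the injection over 5 to 10 seconds"). That is a difference between arms. It is not evidence of a different variance.

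If the outside arms are less variable than the two arms being compared, the primary interval is too narrow. If they are more variable, it is too wide. The same pooled variance enters the SC versus IV comparison, where a misstated IV spread acts in the opposite direction.

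**Working it through.** **Inputs.** 16 completers per arm (Protocol 10.1). SAP 8 defines the PK population by evaluable data ("population will consist of all subjects who received study drug and have evaluable PK data"), so up to 18 per arm may enter. CV 49% for the AUCs. 90% two-sided intervals. No leakage terms. Unequal CVs are assumptions, because the documents give none.

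**Degrees of freedom.** 64 − 4 = 60 in total, 15 per arm. Test IV and Test SC 1 × 2-mL together supply 30 of 60. At 18 per arm the total is 68, with 17 per arm. If IV rows are left out of the model, Test SC 1 × 2-mL still supplies 15 of 45.

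**The plan's own precision.** Log-scale SD = √ln(1 + 0.49²) = √0.2152 = 0.4639. Half-width = t(0.95, df) × 0.4639 × √(2/16): 0.274 at 60 df and 0.278 at 30 df. This reproduces the stated 28% as an expected half-width. The half-width not exceeded with 90% probability multiplies this by √(χ²(0.90, df)/df) and is 0.305 at 60 df. The gap between 0.305 and 28% is a separate matter.

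**Primary contrast if only the IV spread differs.** The expected pooled variance is (45 × 0.2152 + 15 × IV log variance)/60.

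- IV CV 20%: log variance ln(1.04) = 0.0392; pooled 0.1712; SD 0.4138; half-width 0.244 instead of 0.274.
- IV CV 70%: log variance ln(1.49) = 0.3988; pooled 0.2611; SD 0.5110; half-width 0.302.

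**Combined SC versus IV.** The true variance of the estimate is 0.2152/32 + IV log variance/16. The model uses pooled variance × 1.5/16.

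- IV CV 20%: true 0.0092, used 0.0161, so the interval is too wide.
- IV CV 70%: true 0.0316, used 0.0245, so the interval is too narrow.

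**Simulated coverage of the nominal 90% interval** (400,000 trials per case, 16 per arm, SC arms at 49%):

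| Assumed IV CV | Primary, one variance | Combined SC vs IV, one variance | Either contrast, per-arm variance |
|---|---|---|---|
| 20% | 86% | 97% | 90% |
| 30% | 87% | 95% | 90% |
| 40% | 89% | 92% | 90% |
| 49% | 90% | 90% | 90% |
| 60% | 92% | 87% | 90% |
| 70% | 93% | 85% | 90% |

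Primary coverage at 18 per arm agrees within 0.1 point.

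**If Test SC 1 × 2-mL differs instead.** At CV 30% and 70%, primary coverage is 87.0% and 92.9% in the four-arm model, and 85.9% and 93.6% in an SC-only model. Leaving IV out therefore does not remove the dependence.

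**Cost of per-arm variances when all CVs are equal.** Mean half-width goes from 0.2728 to 0.2766 (0.2766/0.2728 = 1.014). The 90%-assured half-length goes from 0.305 to 0.323.

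**Weight, for precision only.** The share of log-AUC variance explained is exponent² × ln(1 + weight CV²)/0.2152.

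- Exponent 0.5, weight CV 15%: 0.25 × 0.02225/0.2152 = 0.026.
- Exponent 1.0, weight CV 20%: 0.0392/0.2152 = 0.182.

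Residual SD is multiplied by √(1 − 0.026) = 0.987 or √(1 − 0.182) = 0.904. The covariate itself costs about 0.9% in the pooled model, so the net factors are 0.987 × 1.009 = 0.996 and 0.904 × 1.009 = 0.912.

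**The case against.** One residual variance on log-transformed PK data is a standard choice, and nothing in the documents shows that the variances differ. This stands: the plan is not wrong, and the unequal CVs above are assumptions.

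The four-arm model is a reading. The list after the single-model sentence holds only two SC contrasts, and Protocol 10.3.2.2 asks for a single model only where possible and describes the absolute-bioavailability effect as SC or IV. This also stands. The unfiltered code makes four arms the natural reading, but an SC-only model is open. In that case the IV coverage figures for the primary contrast fall away, and the dependence on Test SC 1 × 2-mL remains.

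The plan is not wholly silent on diagnostics. The MODEL line requests residuals, and additional analyses are allowed. Neither is a prespecified rule.

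The change widens the 90%-assured half-length from 0.305 to 0.323, further from the stated 28%. That is a real cost.

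Three stronger inferences are tempting but not supported:

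- **Cmax.** A reader might extend the coverage figures to Cmax. The IV comparison is on the AUCs only, and the SAP does not say whether IV rows enter the Cmax model.
- **Combining the SC arms.** A reader might put a false-positive rate on the decision whether to combine them. The plan gives no criterion for an observed effect, so any rate depends on an invented rule.
- **A complete repair.** A reader might conclude that one code line frees every contrast from the other arms. A common weight slope brings them back in. So do the leakage terms, and leakage is recorded only in the two Test SC arms (SAP 9.4.8).

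**Conclusion.** This is a worthwhile, low-cost improvement and not an error. With equal CVs the planned interval is valid. With an assumed IV CV of 20% to 70% and SC arms at 49%, primary AUC coverage runs from about 86% to 93%, and combined SC versus IV coverage from about 97% to 85%, against a nominal 90%. The documents do not show which side applies. These figures rest on the four-arm reading, 16 per arm, no leakage terms and no other covariates. A reader might infer that the primary interval is known to be too narrow; without an IV CV, that cannot be said.

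Weight is a separate and smaller point. The unadjusted ratio is unbiased and its interval valid. The possible gain depends on an assumed exponent of 0.5 to 1.0 and an assumed weight CV of 15% to 20%.

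**What to change.** In SAP 9.3.2, for the AUC contrasts, add `repeated / group=formulation;` and keep the existing `ddfm=kr`. Estimate combined SC versus IV as the average of the two SC arms minus IV, with an explicit ESTIMATE statement. Without covariates this gave about 90% coverage in every AUC case simulated. Grouping by route only, or an SC-only model, is not enough, because Test SC 1 × 2-mL would still be pooled into the primary interval. The cost is one code line, the ESTIMATE statement and matching SAP text. If the variances are equal, the interval is on average 1.4% wider, and the 90%-assured half-length is 0.323 instead of 0.305.

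Separately, prespecify log(screening weight) as a covariate, with the unadjusted model as a sensitivity analysis. Weight is already collected at screening. In the pooled model the interval is about 0.9% wider if weight has no effect, and about 0.5% to 9% narrower under the assumed effects. With both changes, the width relative to the planned model is 1.023 if weight has no effect, 1.010 at the weak end of the assumed range and 0.927 at the strong end. That is from about 2% wider to 7% narrower.
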